University of Texas Medical Branch at Galveston

Research Protocol IRB #21-0327

Title: (Free Foley Trial) Tension versus Tension-Free Foley Balloon for Cervical Ripening in Nullipa-

rous Women Undergoing Induction of Labor: A Cluster Randomized Controlled Trial

Principal Investigator: [name], DO Faculty supervisor: [name]

Funding: Departmental

1. Introduction and Purpose:

Foley balloons are commonly used as a mechanical method of cervical ripening for induction of labor. Foley balloons may be placed either under tension or without tension (tension-free). Currently at UTMB, it is left to the provider to decide which technique is utilized. The purpose of our study is to examine time to delivery in nulliparous women undergoing induction of labor who have a Foley balloon placed as a mechanical cervical dilator, assigned to either tension or without tension. The goal is to determine if there is a potential added benefit to placing the Foley balloon on tension as compared to no tension, both are considered standard of care at our institution. Our hypothesis is that Foley balloon under tension for cervical ripening results in shorter time to vaginal delivery compared to Foley balloon placed without tension.

2. Background:

The rate of induction of labor has increased significantly in the United States. The US National Vital Statistics Report birth data for 2018 reported an induction of labor rate of 27.1% compared to 23% in 2013. 14,15 The rate of induction of labor will likely continue to increase as studies are published demonstrating maternal and neonatal benefits associated with elective 39-week induction of labor. 10 The rate of induction of labor is likely to also continue to increase as the incidence in medical comorbidities continue to increase in the United States. Even though induction of labor occurs in greater than a quarter of births in the United States, significant variation in clinical practice exists in the management of induction of labor. There is significant need to research methods for induction of labor given these shifts in clinical practice and the lack of an accepted standard of care.

Placement of a mechanical dilator is a common method of labor induction. ^{2,3,5,7,8,11,13,16,17,18} Advantages of mechanical dilators over pharmacologic methods include typically lower cost and the ability to discontinue the induction agent in case of fetal distress. The first use of a Foley balloon for cervical dilation was described by Krauss in 1853. The use of a transcervical Foley balloon for labor induction was initially described by Embrey and Mollison. ⁶ The transcervical Foley balloon is the most common method of mechanical dilation utilized at our institution, placed either with or without tension based on provider and nursing practices and preferences. There is not an evidenced-based standard of care protocol for mechanical cervical ripening with a Foley balloon; therefore, significant variation in clinical practice exists between individual providers and institutions. Variations exist in type of balloon (Foley balloon verses double balloon), placement (manual verses visual placement with sterile speculum), the use of concomitant ripening agents, and the use of tension on the balloon.

The use of tension placed on a Foley balloon has been previously examined. Fruhman, G. et al., examined Foley balloon with tension verses Foley balloon without tension with the use of concomitant Pitocin. In addition, an extensive search on clinicaltrials gov revealed another study that is currently recruiting to assess Foley balloon placement with tension verses no tension with the use of concomitant vaginal misoprostol for cervical ripening (NCT03588585). No studies were found that examined the use of a foley balloon with or without tension without the use of concomitant cervical ripening agents for term induction of labor in nulliparous subjects. Both methods are currently being used inconsistently in our labor and delivery unit at UTMB and both are standard of care in our institution. In addition, prior trials examined were not powered for parity.

3. Concise Summary of Project:

This will be a pragmatic cluster randomized clinical trial. The study period will be between February 2022 and February 2023. The number of subjects studied will be 405 subjects at UTMB. The target population for our study is nulliparous women who present for induction of labor at term. If there is a decision by the obstetric team to place a transcervical foley dilator for cervical ripening in a prospective subject meeting inclusion criteria for the study, the obstetric provider will follow the weekly randomization sequence for study group (No Tension) or the control group (Tension) based on the assigned cluster for the entire unit for that week. Both study groups will receive standardized labor management as currently performed at UTMB as Foley balloon placed with tension and without tension are both considered standard of care at our institution. The subjects will receive the same care and expertise as any other patient treated in our unit. See below for more details on study procedures and consenting process.

The Tension standard of care (control group) will undergo induction of labor by placement of a transcervical Foley balloon, which is standard of care at our institution. A Foley balloon will be introduced into the cervix either manually or under direct visualization based on provider preference and training. The balloon tubing will be pulled to create tension and will then be taped to the patient's inner thigh. Balloon tension will be periodically assessed, and tension reapplied if needed as per the unit's standard protocol.

The No Tension standard of care (study group) will undergo induction of labor by placement of a transcervical Foley balloon. A Foley balloon will be introduced into the cervix either manually or under direct visualization as the control group but the foley will not be taped or under tension. The balloon tubing will be left free of tension and will hang freely.

Subjects in the control and study group will then undergo standard intrapartum care. The total participation time in the study will be considered terminated following delivery. Details of the procedure for the control group and study group can be found below.

4. Study Procedures:

Visit#1

4.1 Recruitment, Screening and Consenting:

Recruitment: Subjects will not be recruited, however, we will include records of all nulliparous pregnant subjects admitted to L&D for scheduled induction of labor at term who have had a decision made by their managing clinical team to place a transcervical foley balloon for purposes of mechanical dilation who met inclusion and exclusion criteria listed below.

2 V4.1 Protocol Version Date: 02/28/2023

Screening: Subject records will be screened and included if they met inclusion and exclusion criteria at the time a decision to place a transcervical foley balloon with or without tension under the randomized sequence for purposes of mechanical dilation was made in labor and delivery.

Consenting process: Subjects will not be consented; we are requesting a waiver of patient consent. However, we will be obtaining written consent from all faculty providers that practice in our unit, relinquishing the standard of care method for placement of Foley balloon with tension versus no tension to a controlled randomized process before initiation of the trial. The provider consent form is attached in the application. Subjects will not be consented for the study; however, subjects will be verbally informed about the methods used for induction of labor. Providers placing the Foley balloon will obtain verbal consent for labor induction with Foley balloon with tension or without tension, which is the current standard of care. Written consent to participate in this study will be obtained from the faculty who agree to allow their patients to participate in this research protocol. Providers may withdraw individual patients from the study if the provider no longer deems that participation is in the best interest of the individual.

Justification of waiver:

Consent for research will not be obtained as this study involves two standards of care that are currently being performed at UTMB. A waver of informed consent will be submitted with the IRB application. However, we will be obtaining written consent from all providers (see attached document and more information below).

The primary risk of participation in the study is breach of confidentiality. The waiver of consent for research is appropriate because no contact between the study team and subjects will take place outside of standard clinical care. All subjects will receive one of two standards of care, which are currently selected per providers choice for placing the Foley balloon either under tension (tubing taped to thigh) or without tension (tubing hangs free). We feel this study is of minimal risk, as subjects would normally receive this standard of care through an uncontrolled randomized process of provider's choice, which inconsistently varies between tension vs. no tension. Randomizing the method of tension versus no tension in a controlled process, will allow data to be effectively analyzed to assess if one method is best for subjects. Both methods of induction utilized are approved by the American College of Obstetricians and Gynecologists, and it is not currently known if one method is inferior to the other.

Additionally, we will be obtaining written consent from all providers that practice in our unit, relinquishing the standard of care method of Foley balloon placement with tension or no tension to a controlled randomized process before initiation of the trial. The provider consent document is attached in the IRB application.

The cluster randomized trial design is such that each week, the chosen method of induction of labor in subjects meeting inclusion criteria is randomized to either:

- Foley balloon with tension which is current standard of care (control group)
- Foley balloon without tension (tension free) which is also a current standard of care (study group).

To summarize:

- A waiver of patient consent for research is requested
- No subjects will be consented for research

- Written medical consent for delivery will be obtained from all subjects per standard of care
- The risks and benefits of induction of labor will be discussed with each patient prior to obtaining medical consent for delivery, which is consistent with the current standard of care.
- In addition subjects will be verbally informed the type of labor induction they will receive, (which is also consistent with current standard of care):
 - Foley balloon with tension (tubing taped to thigh)
 - o Foley balloon without tension (tubing hangs free)
- Written research consent will be obtained from all providers to follow weekly randomization of tension vs. no tension
- The two methods of induction being compared (tension vs. no tension) are currently accepted and considered standard of practice for women with an unfavorable cervix who require induction of labor.

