4.2. Operationalization

Randomization

This study will use cluster randomization, with each week group described as a cluster. Prior studies have investigated induction of labor methods utilizing cluster randomization. Cluster randomization will be computer generated and will assign each cluster (weeks) to the control or study group. Both the study group and the control group are considered part of the standard of care for induction of labor at UTMB. Clusters will be block randomized in groups (weekly).

Labor and Delivery Unit/Staff

Several training sessions will occur to notify all staff of the trial and the protocol. Training sessions will include a copy of the protocol to review as well as follow-up email communication. The PI will also be available for questions. All operations will be also reviewed with all staff.

At shift change 0630-0700 am and pm every Monday to Friday, randomization assignments will be announced to all nurses and providers on the Labor and Delivery unit. All staff caring for subjects during the week of randomization will be notified of the cluster randomized for that week for all labor inductions. Notifications and plastic tags will be placed in the workstations for the providers and at all nursing stations on labor and delivery and at the patient's room door stating Tension or No Tension. A notification will also be placed at the work station of the study team. All study team in the Perinatal Research Department will also be notified via email at the beginning of each week.

An Epic order will be placed by provider specifying "Foley balloon under tension" or "Foley balloon No Tension" according to the randomization assignment.

Subjects under treatment conditions before this time will be included as part of the treatment block assignment at the time of inclusion and will not be allowed to cross over. The subject will be included in the analysis by intention-to-treat once the randomization assignment has been made.

The cluster randomized trial design is such that each week, the chosen method of induction of labor in subjects meeting inclusion criteria is randomized to either the Tension standard of care (control group) or No Tension standard of care (study group). All subjects who would meet inclusion criteria for foley balloon induction of labor will be participants in the study. The two methods of induction being compared are currently accepted and practiced standards used for women with an unfavorable cervix who

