4.3. Placement of Foley Balloon

The control group will undergo induction of labor by placement of a transcervical Foley balloon, which is standard of care at our institution. A Foley balloon will be introduced into the cervix either manually or under direct visualization with a sterile speculum exam based on provider preference and training. The balloon will be filled with 60 ml of sterile 0.9% NaCl. Proper placement will be confirmed manually. The balloon tubing will be pulled to create tension and will then be taped to the patient's inner thigh. The foley balloon will be left in place on tension for at least 12 hours, and no longer than 24 hours. Balloon tension will be periodically assessed, and tension reapplied if needed.

The study group will undergo induction of labor by placement of a transcervical Foley balloon as the control group. A Foley balloon is introduced into the cervix either manually or under direct visualization as the control group but the foley will not be taped or under tension. The balloon tubing will be left free of tension and will hang freely.

Additional information regarding management of the foley balloon in both the study and control group:

- Placement of the Foley balloon will be performed by the managing obstetrical team.
- The Foley balloon will be left in place for at least 12 hours, and no longer than 24 hours.
- Balloon will be assessed close to 12 hours following placement in all participants.
- The balloon may be assessed prior to the 12 hours for a variety of reasons including, for example, patient request, changes in fetal heart tracing, increased reported pain, and spontaneous rupture of membranes. The reason for checking prior to twelve hours will be documented.
- Following expulsion or removal at 12 hours, sterile vaginal exam will be performed. Patient will then undergo standard intrapartum care.
- If cervix remains unfavorable after extraction of the foley balloon at 12 hours (< 3cm and at most 60% effaced), a second Foley balloon will be used in this case for a maximum of 12 hrs. No crossover will be allowed. In other words, a second Foley balloon will be placed in the same manner as the first assignment arm.
- If the Foley balloon is unable to be placed in either insertion technique, a prostaglandin agent for cervical ripening may be used and insertion of the mechanical dilator can be re-attempted at a later time, as is the standard of care at our institution. No cross over will be allowed.

Visit#2

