4.6. Withdrawals

[figure not shown]
Subjects who withdraw from the study will be excluded from further follow-up. Outcomes ascertained up until the time of withdrawal will be reported in intention-to-treat fashion. The patient will be withdrawn from the study if she wishes to discontinue participation. If any of the exclusion criteria listed above are met, or condition changes that leads to inclusion criteria not being met anymore, data collection will be terminated, and the patient will be withdrawn from the study.

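### A woman withdrawn before delivery loses her delivery outcomes under Section 4.6, although providers who know the arm may withdraw her and the plan promises intention-to-treat analysis from assignment

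*Combined protocol and SAP*

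**What the plan says.** - **Who may withdraw a woman.** Section 4.1 (Consenting process): "Providers may withdraw individual patients from the study if the provider no longer deems that participation is in the best interest of the individual". It sets no criteria and does not require a reason to be recorded. Section 4.6 adds the woman's own choice: "The patient will be withdrawn from the study if she wishes to discontinue participation".
- **What staff know.** Section 4.2: "randomization assignments will be announced to all nurses and providers on the Labor and Delivery unit". The arm is also posted at workstations, nursing stations and the patient's door.
- **What happens to the data.** Section 4.6: "Subjects who withdraw from the study will be excluded from further follow-up", followed by "Outcomes ascertained up until the time of withdrawal will be reported in intention-to-treat fashion".
- **Who is analysed.** Section 4.2: "The subject will be included in the analysis by intention-to-treat once the randomization assignment has been made". Section 12 also calls the analysis intention-to-treat. It gives no method for missing outcomes, and its sample size assumes complete ascertainment.
- **When outcomes arise.** The primary outcome (Section 4.8) runs from first balloon placement to delivery. Of the secondary outcomes in Section 4.9, cesarean, postpartum hemorrhage, endometritis, neonatal infection, Apgar scores, NICU admission and neonatal stay can be known only at or after delivery.
- **Where data come from.** Electronic records (Section 7), with charts reviewed to 30 days postpartum (Section 4.4). Patient consent for research is waived, and the study team has no contact with women outside usual care (Section 4.1).

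**The concern.** Section 4.6 treats leaving the study as the end of data collection, in a trial where the data come from the chart and the main outcome lies in the future for any woman withdrawn during ripening or labor. Reporting what was ascertained before withdrawal does not rescue the analysis, because for the primary outcome nothing has yet been ascertained. The label intention-to-treat then covers a comparison of women who were not withdrawn.

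The decision to withdraw is made during the induction by someone who knows the arm. Section 4.3 itself lists pain, fetal heart rate changes and patient request as events expected while the balloon is in place. Such events could prompt a withdrawal and could also be related to how long labor takes. Tubing taped under tension and tubing left hanging need not prompt them equally. If they do not, the women missing from one arm differ from those missing from the other, and the difference in mean time is biased. Cesarean, hemorrhage, infection and neonatal outcomes would be missing for the same women.

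**Working it through.** **1. The plan's own figure.** Inputs, all from Section 12: means 1053.399 and 1316.74 min, SD 535.73 min, two-sided alpha 0.05, power 80%, 10 women per cluster, rho 0.1.

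- Planned difference: 1316.74 − 1053.399 = 263.34 min.
- Women per arm without clustering: 2 × [535.73 × (1.960 + 0.842) / 263.34]² = 64.97.
- Design effect: 1 + (10 − 1) × 0.1 = 1.9. Then 64.97 × 1.9 = 123.4, and 123.4 / 10 = 12.34, rounded up to 13 clusters or 130 women per arm. This matches the plan.
- With rho = 0: 64.97 / 10 = 6.50, rounded up to 7 clusters per arm, 140 women in total. This also matches.

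No step allows for lost outcomes.

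**2. Loss unrelated to outcome.** With 405 women in 26 clusters, mean cluster size is 405 / 26 = 15.58, the design effect is 1 + 14.58 × 0.1 = 2.458, and the effective number per arm is 202.5 / 2.458 = 82.4. Power is 88.4%. If 10% or 20% of all women are lost at random, power is 87.1% or 85.5%. At the minimum of 130 per arm the values are 82.0% with no loss, 80.0% at 10% and 77.6% at 20%. Random loss is therefore not the main issue.

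**3. Loss related to outcome.** Let w be the share of one arm withdrawn and D the mean difference in time between withdrawn and retained women. The full-arm mean is (1 − w) × m + w × (m + D) = m + wD, where m is the mean of those retained. The observed arm mean is therefore off by w × D. Neither w nor D is in the documents, so both are assumptions. D is taken as 0.5, 1 and 1.5 times the planning SD.

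| Withdrawn, one arm only | D = 268 min | D = 536 min | D = 804 min |
|---|---|---|---|
| 5% | 13.4 min (5.1% of 263.34) | 26.8 min (10.2%) | 40.2 min (15.3%) |
| 10% | 26.8 min (10.2%) | 53.6 min (20.4%) | 80.4 min (30.5%) |

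The net bias in the comparison is w × D in one arm minus w × D in the other. It is zero if both arms lose the same share of similar women.

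**4. Consequence for the test** (405 women, 26 clusters, rho 0.1, loss in one arm only).

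- If the shift is toward no difference, power falls from 88.4% to 84.6%, 80.5% and 75.8% across the 5% row, and to 80.2%, 70.2% and 58.4% across the 10% row.
- With no true difference, the two-sided type I error is about 5.3%, 6.2% and 7.7% across the 5% row, and about 6.2%, 9.7% and 15.9% across the 10% row.

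**5. Direction.** If withdrawn women would have taken longer, the affected arm looks faster than it is. In the no-tension arm this shrinks the hypothesised difference. In the tension arm it enlarges it.

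**The case against.** **Section 4.6 does not name provider withdrawal.** This is true. It speaks of subjects who withdraw and then names the woman's choice and loss of eligibility. But no other text says what happens to a woman whom the provider withdraws, so either Section 4.6 applies to her or the plan has no rule. Both need the same repair.

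**Follow-up might mean something other than abstraction.** Only for loss of eligibility does the section say outright that "data collection will be terminated, and the patient will be withdrawn from the study". However, the sentence limiting reported outcomes to those ascertained before withdrawal leaves little room for abstracting a later delivery time. (The eligibility clause is a separate matter and is not part of this point.)

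**A reader might infer that every woman taken off the assigned technique loses her outcome, because withdrawal is the only way out.** The documents do not support this. No text makes leaving the technique a withdrawal, and Section 4.2 keeps her in the analysis. In Section 4.3, "No crossover will be allowed" concerns placement of a second balloon. The similar statement there concerns failed insertion, and the one in Section 4.2 concerns women already under treatment when an assignment is announced. Section 4.3 also allows an early check of the balloon for pain or fetal heart changes, with the reason documented and no mention of withdrawal.

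**A reader might also infer that a woman who wishes to stop can only be refusing the balloon or the tape, since no woman is consented for research.** That goes too far. Section 10 speaks of a subject accepting participation, so she may be objecting to the study itself.

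**The size is assumed.** This stands. The rate, the excess time, the one-arm pattern and the direction are all unknown. The illustration also gives every withdrawn woman a delivery time, whereas Section 4.8 specifies vaginal delivery and some might deliver by cesarean.

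**It may be too late to record reasons prospectively.** This is probably right. The addendum to Section 12 reports 17 clusters completed between June 6 and October 3, 2022. At one cluster a week, the remaining 9 would have ended in early December 2022, before this version's date of 02/28/2023. The remedy may have to be largely retrospective.

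**Conclusion.** The point holds for women withdrawn from the study before delivery, by the provider or at their own request. For them the stated rule leaves no primary outcome and none of the outcomes that arise at or after delivery. That contradicts intention-to-treat inclusion from assignment and the complete ascertainment behind the sample size. It does not extend to women who depart from the technique but remain in the study.

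The contradiction is in the text; the size of its effect is not. Under assumed one-arm withdrawal of 5% to 10% and a difference of 0.5 to 1.5 SD, the affected mean moves by about 13 to 80 min, or 5% to 31% of the planned difference. With few withdrawals, or balanced withdrawal of similar women, the effect would be small or nil. The enlarged sample protects against random loss but not against this bias. The conclusion for provider withdrawals rests on reading Section 4.6 as covering them.

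**What to change.** Reconcile Sections 4.1, 4.2, 4.6 and 12 by stating in Section 4.6 that:

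- withdrawal by a provider or at a woman's request does not end chart abstraction;
- she stays in her assigned week and arm for the analysis;
- her delivery, maternal and neonatal outcomes are abstracted through the 30-day chart review already planned, retrospectively for women already withdrawn where the IRB permits;
- abstraction ends only if she explicitly objects to use of her records.

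Report withdrawals by arm, with time and reason where documented. If delivery times are recovered for all withdrawn women, this source of bias disappears.

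The change concerns data handling only. It says nothing about when a provider may depart from the assigned technique.

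The cost is an IRB amendment and abstraction of a few more charts from records the study already uses, with no new visits or patient contact. Whether the IRB would allow abstraction for women already withdrawn cannot be judged from the documents.
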